3.2.2. OMERACT-OARSI Response

The OMERACT-OARSI response ([Pham et al. 2003](#)) is defined as follows:

- A. High improvement from baseline in pain or function greater than or equal to 50% and absolute change of at least 20 points [scaled on a 0-100 range], OR
- B. Improvement from baseline in at least two of the following
 - pain greater than or equal to 20% and absolute change of at least 10 [scaled on a 0-100 range]

- function greater than or equal to 20% and absolute change of at least 10 [scaled on a 0-100 range]
- Patient Global Assessment greater than or equal to 20% and absolute change of at least 10 [scaled on a 0-100 range]

Additionally, the OMERACT-OARSI “strict” response is defined by any response satisfying the above condition A only.

Both OMERACT-OARSI response and OMERACT-OARSI “strict” response are efficacy outcome measures in this study. WOMAC Pain and WOMAC Function subscores will be utilized and scaled appropriately to calculate the OMERACT-OARSI response.

3.2.3. Patient Global Assessment of Disease Activity

The patient assessment will be a 100 mm VAS scale adapted from the Patient Assessment Form © 1999, American College of Rheumatology. The subject will rate how well they are doing, considering all the ways in which illness and health conditions may affect him/her. The VAS scale will be anchored by “Very Well” on the left and “Very Poorly” on the right.

3.2.4. Physician Global Assessment of Disease Activity

The physician assessment will be a 100 mm VAS scale adapted from the Physician Assessment Form © 1999, American College of Rheumatology. The investigator will rate the subject’s disease activity. The VAS scale will be anchored by “Very Good” on the left and “Very Bad” on the right.

3.2.5. Joint Space Width (JSW)

JSW in the target knee will be assessed by radiograph. A radiograph may be repeated if the image quality of the original radiograph is deemed unsatisfactory by the imaging vendor, Medical Metrics, Inc. (MMI), according to Image Review Charter. The radiograph with the best image quality (where applicable) will be used for analysis as long as it was taken within the visit window. If two or more radiographs for the same study visit are assessed as having the same image quality, the earliest radiograph will be considered for that visit. Medial and lateral joint space width measurements will be provided by the vendor.

3.2.6. Health-Related Quality of Life

Overall HRQOL will be assessed with the SF-36 Version 2 questionnaire which consists of 36 questions that are asked of the subject. The subject’s responses will be used to calculate norm-based scores for eight scales (physical functioning, role-physical, bodily pain, general health, vitality, social functioning, role-emotional, mental health) and two component summary measures (physical health, mental health). Scoring software provided by the SF-36 vendor, Optum, will be utilized to calculate the standardized scores.

4. ANALYSIS SETS

4.1. Intent-to-Treat Analysis Set

The Intent-to-Treat (ITT) Analysis Set includes all subjects who were randomized.

4.2. Modified Intent-to-Treat Analysis Set

The Modified Intent-to-Treat (mITT) Analysis Set includes all ITT subjects who received a protocol specified dose of SM04690 or placebo, analyzed as treated. Subjects incorrectly receiving doses not prescribed by the protocol are excluded from this analysis set.

4.3. Per Protocol Analysis Set

The Per Protocol (PP) Analysis Set includes all ITT subjects who complied with all study procedures and evaluations and did not have major protocol deviations.

4.4. Safety Analysis Set

The Safety Analysis Set includes all subjects who were exposed to study product.

5. STATISTICAL CONSIDERATIONS

5.1. Interim Analysis

By definition, “[a]n interim analysis is any analysis intended to compare treatment arms with respect to efficacy or safety at any time prior to formal completion of a trial” ([ICH E9 Guidance 1999](#)). Analysis of the specified efficacy endpoints (Section 8.2) will be conducted after all subjects complete the Week 26 visit but prior to the formal completion of the trial at 52 weeks. Thus, by definition, these efficacy analyses will be described as an interim analysis. However, no trial adaptation(s) will be made based upon the results of the interim analysis.

The datasets supporting this analysis will be validated from a snapshot of the raw study database. Source data verification of the raw data supporting the interim analysis as well as query resolution will be completed before unblinding for the interim analysis. All available data supporting the Week 26 JSW analysis (i.e. radiographs) will be measured by the imaging vendor and included in the snapshot dataset prior to unblinding for the interim analysis. In addition, all available safety events occurring up to and including the Week 26 visit will also be included in the snapshot dataset prior to unblinding and summarized in the interim analysis report.

All available data in support of the interim analysis will be dated and sequestered from the final analytical databases. Any changes made to the sequestered data in the raw database after the interim analysis that impacts any outcome within the interim efficacy analysis will be summarized in the clinical study report.

5.2. Handling of Missing Data

Multiple imputation will be utilized for the primary and secondary analyses. Missing data will be imputed based upon the observed data for each outcome under the missing at random (MAR) assumption following the paradigm first developed by Rubin (Schafer 1999). The imputation will adjust for the outcome’s baseline data in a regression model with data imputed independently for each timepoint; any missing baseline data will also be imputed. A total of 10 imputation datasets will be created and analyzed based upon accepted convention (Schafer 1999). Error estimates of the multiple imputation itself as well as an overall summary of the efficacy analysis will be averaged across the 10 imputed datasets based upon Rubin’s paradigm.

Specifically, let Q denote the imputed mean of an efficacy outcome Y subject to missing data at a given timepoint, where the estimate of that mean for any i^{th} imputation would be defined as function of both observed and missing data such that

$$\widehat{Q}^{(i)} = E\left(Q^{(i)} | Y_{observed}, Y_{missing}^{(i)}, Y_{Baseline}, I(Group)\right), i = 1, \dots, 10.$$

After all 10 datasets have been imputed, the overall estimate of Q is a simple average defined as

$$\bar{Q} = \frac{\sum_{i=1}^{10} \widehat{Q}^{(i)}}{10}.$$

For this analysis using 10 imputed datasets, the variance of \bar{Q} is defined as

$$Var(\bar{Q}) = 1.1B + \bar{U}$$

where B is the between imputation variance and U is the within imputation variance:

$$B = \frac{1}{9} \sum_{i=1}^{10} (\widehat{Q}^{(i)} - \bar{Q})^2;$$

$$\bar{U} = \frac{\sum_{i=1}^{10} U^{(i)}}{10}.$$

Imputations will be performed with a seed of 201610141.

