In this study, general medical evaluations and recording of vital signs will be performed at all visits. A pain VAS will be administered at the Screening Visit. X-ray imaging of the target knee joint will be performed at screening and at Weeks 26 and 52 (EOS)/Early Termination. A Widespread Pain Index and Symptom Severity Score assessment will be conducted at the Screening Visit only. Physical examinations will be performed at the Screening Visit (including knee examination), Day 1, Week 13, Week 26, Week 39 and Week 52 (EOS)/Early Termination. Clinical laboratory evaluations will be performed at the Screening Visit, Week 13, Week 26, Week 39 and Week 52 (EOS)/Early Termination. The subject will complete the WOMAC questionnaire, Patient Global Assessment, and SF-36 at all visits; the investigator or designated study staff will complete the Physician Global Assessment at all visits. Recording of signs and symptoms of study medication intolerability and adverse event reporting will start following the injection of the study medication and continue until the subject completes follow-up visit Week 52 (EOS)/Early Termination. All AEs, whether volunteered, elicited, or noted during examination, will be recorded throughout the study.

An interim analysis will be performed after all subjects have completed their Week 26 visit; however clinical study sites and subjects will remain blinded throughout the study.

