2.1. Sample Size

A sample size of approximately 445 subjects will be randomized at a ratio of 1:1:1:1 (0.03 mg active per 2 mL injection : 0.07 mg active per 2 mL injection : 0.23 mg active per 2 mL injection : placebo). The sample size for this study was based upon accepted statistical practice to establish an acceptable level of precision with respect to treatment effect estimation ([Piantadosi 1997](#)).

To explore possible power expected from this study design, an analysis of covariance regression model was simulated via a Monte Carlo simulation of 1000 replicates. The simulation model estimated a change in WOMAC Pain from baseline comparison between SM04690 and placebo adjusting for baseline WOMAC Pain. The following assumptions were made for the power simulation:

- Sample size of 100 subjects per group,
- Type 1 error rate of 5%,
- WOMAC Pain Baseline average is 11 points [scale 0-20] with a standard deviation of 3,
- WOMAC Pain Baseline is the same for both treatment and placebo groups,
- Treatment change from baseline is -5.8 points, leading to a final score of 5.2 points [scale 0-20]
- Historical placebo change from baseline is -3.5 points, leading to a final score of 7.5 points [scale 0-20]
- Final pain score has standard deviation of 4 and is the same for both treatment and placebo groups, and
- Correlation between baseline and final pain score is 0.1.

The WOMAC Pain subscore parameters were based upon observed data from the 0.07 mg group in SM04690-01. Based upon these assumptions, SM04690-OA-02 is estimated to have 95.8% power.

A simulation model for WOMAC Function was also estimated. The following assumptions were made for the power simulation:

- Sample size of 100 subjects per group,
- Type 1 error rate of 5%,
- WOMAC Function Baseline average is 39 points [scale 0-68] with a standard deviation of 11,
- WOMAC Function Baseline is the same for both treatment and placebo groups,
- Treatment change from baseline is -19.5 points, leading to a final score of 19.5 points [scale 0-68]
- Historical placebo change from baseline is -13.5 points, leading to a final score of 25.5 points [scale 0-68]
- Final function score has standard deviation of 15 and is the same for both treatment and placebo groups, and
- Correlation between baseline and final function score is 0.1.

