3.2.1. Western Ontario and McMaster Universities Arthritis (WOMAC) Index

The WOMAC NRS3.1 instrument is a patient reported outcome measure to assess the symptoms of OA. Subjects will be asked to complete the WOMAC instrument based on their symptoms in the target knee.

The WOMAC consists of 24 questions in three domains: physical function (17 questions), pain (5 questions) and stiffness (2 questions). The response for each question in the NRS format ranges from 0 to 10. Each domain subscore as well as a total score are calculated by adding together the numerical responses. Subsequently, the WOMAC NRS3.1 ranges from 0 to 240 total points.

If any response is missing, the score for that domain (i.e. physical function, pain, or stiffness) as well as the WOMAC Total score will not be able to be calculated.

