5.2.1. Tipping Point Analysis

The MI paradigm, as proposed by Rubin, does not require nor assume any specific assumption about the nature of the missing data. Further, imputations can be (theoretically) created under any assumption of missing mechanism. A sensitivity analysis will be conducted using the tipping point approach to evaluate the robustness of the primary analysis with multiple imputation under the MAR assumption. With the tipping point approach, several additional multiple imputation datasets are created, each departing slightly from the original assumptions used in the primary analyses. The intended result is to establish a certain point in which the new shifted imputations have “tipped”, or overturned, the original conclusions from the primary analysis (i.e. a statistically significant result is now not statistically significant). The magnitude of the shift required to tip the analysis are then evaluated for plausibility; an implausible shift will lead to the conclusion that the multiple imputation analysis is robust to the departure from MAR assumption.

Tipping point analysis will be conducted only for the dose group(s) that is/are statistically significant under the MAR assumption. Based on the SM04690 Phase I study, the placebo change in WOMAC pain from baseline was observed at -3.5 points. When scaled to the NRS format, this translates to a -8.75 reduction in WOMAC pain. The primary analysis will be reassessed by shifting the mean change in WOMAC pain in the treatment group by intervals of +0.5 until the historical placebo threshold of -8.75 (or the placebo response observed in SM04690-OA-02, whichever is more conservative) is reached and/or surpassed. Intervals of +0.1 may further be explored in order to determine a more precise shift parameter for the tipping point. An implausible shift parameter is defined as one that results in the magnitude of change in WOMAC pain in the treatment group to equal or worse than historical (or SM04690-OA-02, again whichever is more conservative) placebo change.

Imputations for the tipping point analysis will be performed with a seed of 201610142.

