8.1.1. ANCOVA Model for Continuous Efficacy Outcomes

ANCOVA models will be used for all continuous efficacy outcome measures summarized by change from baseline in order to test the following three hypotheses:

$$H_0: (\beta_i - \beta_0) = 0$$

$$H_A: (\beta_i - \beta_0) \neq 0, \text{ where } i = 1,2,3$$

In the statement above, β is the least squares estimate in the change in the continuous efficacy outcome from baseline at each timepoint (where β_0 is the estimate for placebo), and i represents each of the three SM04690 treatment groups.

Least squares estimate of difference between each treatment group and placebo in the change in the continuous efficacy outcome from baseline at each timepoint, adjusted for baseline value, will be reported along with unadjusted 95% confidence intervals and P values.

Continuous efficacy measures to be analyzed by the ANCOVA model include:

- WOMAC Pain
- WOMAC Function
- WOMAC Total
- Patient Global Assessment
- Physician Global Assessment
- Medial and Lateral Joint Space Width
- SF-36

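### SAP 5.2 imputes each symptom endpoint visit by visit from baseline, leaves out earlier-visit scores already collected, and does not settle whether treatment group is in the model

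*SAP*

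**What the plan says.** SAP 5.2 applies multiple imputation to the primary and secondary analyses: "Missing data will be imputed based upon the observed data for each outcome under the missing at random (MAR) assumption". The regression adjusts for the outcome's "baseline data in a regression model with data imputed independently for each timepoint". Baseline is the only predictor named there. The section continues "let Q denote the imputed mean of an efficacy outcome Y subject to missing data at a given timepoint", and the expression that follows conditions on baseline and a group indicator. That is the only place where group appears.

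Other sections that bear on this:

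- Protocol 3: "The subject will complete the WOMAC questionnaire, Patient Global Assessment, and SF-36 at all visits". Week 4 scores therefore exist before Week 13, and Weeks 4 and 13 before Week 26.
- SAP 8.1.1: the analysis is an ANCOVA at each timepoint, with dose-minus-placebo differences "adjusted for baseline value, will be reported along with unadjusted 95% confidence intervals and P values".
- SAP 2.1: "Correlation between baseline and final pain score is 0.1".
- SAP 3.2.1 and 5.4 add routes to a missing score besides a missed visit. "If any response is missing, the score for that domain" cannot be computed, and early-termination scores outside a visit window are not assigned to that visit.
- SAP 5.2.1: "Tipping point analysis will be conducted only for the dose group(s) that is/are statistically significant under the MAR assumption". It reassesses the primary pain analysis only.

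**The concern.** Missing at random is only as credible as the variables the imputation conditions on. Here that is a baseline score which, at the SAP's own correlation of 0.1, explains 0.1² = 1% of the variance in final pain. A subject who leaves after a poor Week 4 score is imputed as average for that baseline (and arm, if group is in the model).

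The text supports two readings:

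- **Group in the imputation model.** Its terms match the ANCOVA, so for missing outcomes the imputation adds nothing to a complete-case analysis. If the mechanism or rate of loss differs by arm, the difference is biased: toward the drug if high-pain subjects are lost from the dose arm, against it if they are lost from placebo.
- **Group left out.** Subjects with missing data in every arm are imputed from a pooled mean, and all differences shrink even under completely random loss.

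The symptom endpoints account for 18 of the 21 tests in SAP 8.2.1. Medial JSW (H6, H7, H9) is different: no X-ray is scheduled between screening and Week 26, so there is no earlier follow-up value to add. The tipping-point analysis is a partial safeguard. A dose that misses significance because of placebo-side loss never receives it, and the 15 symptom tests after H1–H3 have no missing-data sensitivity analysis of their own.

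**Working it through.** **The plan's own figures.** The variance factor for 10 imputations is 1 + 1/10 = 1.1, as in SAP 5.2. A two-sided 5% ANCOVA on the SAP 2.1 inputs (100 per group) gives:

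- pain: 2.3 / (4 × √0.99 × √(2/100)) = 4.09, power 98.3% (SAP: 95.8%)
- function: 6 / (15 × √0.99 × √(2/100)) = 2.84, power 81.1% (SAP: 78.5%)

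The gap of about 2.5 points is a separate matter; nothing below depends on it.

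**Inputs from the documents.** About 445/4 ≈ 111 per arm. SAP 5.2.1 scales by 2.5 (−3.5 becomes −8.75), so pain has effect 2.3 × 2.5 = 5.75 and SD 10, and function has effect 15 and SD 37.5. Baseline correlation is 0.1.

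**Assumed, because the documents give no figure.** 10% missing; Week 4–Week 13 correlation r of 0.5–0.7; odds of being missing multiplied by 2 to 4 per SD of pain; selection in one arm only.

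**Group in the model, loss driven by Week 4 pain.** The imputed arm mean equals the completers' mean, so

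bias = p/(1−p) × (mean standardised Week 4 score among the missing) × r × SD

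- odds ×2, r = 0.5: 0.1/0.9 × 0.60 × 0.5 × 10 = 0.33
- odds ×4, r = 0.7: 0.1/0.9 × 1.04 × 0.7 × 10 = 0.81

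Simulated bias in points at Week 13 (4 million draws), as planned / with Week 4 added:

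| Loss driven by | ×2, r 0.5 | ×2, r 0.7 | ×4, r 0.5 | ×4, r 0.7 |
|---|---|---|---|---|
| Week 4 | 0.32 / 0.01 | 0.45 / 0.01 | 0.56 / 0.01 | 0.81 / 0.00 |
| Weeks 4 and 13 equally | 0.57 / 0.30 | 0.60 / 0.19 | 0.99 / 0.54 | 1.06 / 0.36 |
| Week 13 only | 0.66 / 0.51 | 0.66 / 0.35 | 1.14 / 0.89 | 1.14 / 0.62 |

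Adding Week 4 removes essentially all of the bias in the first row, 45–69% in the second and 23–47% in the third. For Week 26 with Weeks 4 and 13 added, the corresponding shares are about all, 51–74% and 31–56%.

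With 111 per arm, 10 imputations and 1,500 trials per scenario, planned imputation with group and complete-case analysis agreed within 0.01 in all 12 scenarios.

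**Other assumptions, loss driven by Week 4**

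- Odds ×1.5: 0.20–0.27.
- r = 0.3: 0.1/0.9 × 0.60 × 0.3 × 10 = 0.20 at odds ×2, and 0.35 with 1.04 in place of 0.60.
- Half the missing values unrelated to pain: 0.17–0.44.
- Both arms selective, 15% versus 5% missing: 0.32–0.72.
- Equal mechanism and rate: about 0.

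**Power if the Week 4-driven loss is in placebo.** The standard error at 10% missing is 1.41 for pain and 5.28 for function.

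- Pain: 5.75/1.41 gives 98%; (5.75 − 0.32)/1.41 gives 97%; (5.75 − 0.81)/1.41 gives 94%.
- Function: bias is 3.75 times larger (1.2–3.0). 15/5.28 gives 81%; 13.8/5.28 gives 74%; 12.0/5.28 gives 62%.

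**Group left out, loss completely at random.** Each arm mean becomes (1−p) × its own mean + p × the pooled mean, so the difference is (1−p) × the true difference. Simulation used four arms of 111, all doses at the planned effect, 10 imputations and 2,000 trials.

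| Missing | Pain, formula (simulated) | Function, formula (simulated) | Function power, group in → out |
|---|---|---|---|
| 5% | 5.46 (5.45) | 14.25 (14.27) | 84% → 79% |
| 10% | 5.18 (5.19) | 13.50 (13.45) | 80% → 74% |
| 15% | 4.89 (4.90) | 12.75 (12.78) | 78% → 67% |

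**The case against.** The strongest reply has five parts.

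1. **Group is probably in the model**, because the expression for the mean conditions on baseline and group together. This stands as the likelier reading, so the dilution figures should not carry the main weight. The per-protocol set would also largely escape dilution. But the sentence specifying the regression does not name group, and the two readings give different answers.
2. **One-arm selection is a chosen scenario.** A dropout rule shared by all arms is plainer. With a real effect, a shared rule gives unequal rates and only attenuates, by about 0.10–0.43 points if the full effect is present at Week 4. That is fair: a shared rule works against the drug and does not create a false positive. Adding Week 4 removes this bias too.
3. **The tipping point covers the false-positive direction for pain.** At the planned change of −5.8 × 2.5 = −14.5, the shift to −8.75 spans 5.75 points. The Week 4-driven biases correspond to imputed values too favourable by bias/0.1 = 3.2, 4.5, 5.6 and 8.1 points. If the shift is applied to imputed values, it spans three of the four. It offers nothing for a dose that wrongly misses.
4. **Most later tests are gated further.** Of the 15 later symptom tests, 13 also sit behind two or three medial JSW tests; only H4 and H5 do not. This narrows the practical reach, though not the reach of the imputation rule.
5. **The effect at H1 is small**, treatment is a single injection, and retention is encouraged. The effect at H1 is small under these assumptions, but function has less power to spare.

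**Conclusion.** The point holds. SAP 5.2 uses no earlier-visit score for the symptom endpoints and does not settle whether group is in the imputation model.

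With group in, bias in Week 13 pain ranges from about 0 (equal mechanism and rate across arms) to 0.32–0.81 points (6–14% of 5.75, or 0.23–0.57 standard errors) for one-arm, Week 4-driven loss at 10% missing and r = 0.5–0.7. It is larger if loss also depends on Week 13 pain, and earlier visits then correct only part of it. The precision gain from adding Week 4 is small; the case rests on bias. With group out, every symptom difference shrinks by the missing fraction.

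The textual finding is firm, while the sizes rest on assumed missingness and correlations. The study is exploratory and the interim analysis triggers no adaptation, so this should be fixed but is not fatal.

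**What to change.** In SAP 5.2, state that for WOMAC pain, WOMAC function and Patient Global the imputation model includes treatment group (or is run separately by arm), baseline, and all earlier observed visits of the same outcome. Impute in sequence (Week 4, then Week 13, then Week 26) or jointly. For medial JSW, state only that group is in the model. Keep the tipping-point analysis, because earlier visits do not deal with loss that depends on unobserved pain.

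The cost is SAP wording, a little code and a slightly larger imputation model, settled before unblinding for the Week 26 analysis. It needs no new data, visits or subjects.

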8.2.1. Familywise Error Rate Control

The familywise error rate for the interim efficacy analyses will be controlled in the strong sense using the closed, fixed sequence testing method ([Dmitrienko et al 2010](#)). All hypothesis tests will be evaluated in the pre-specified sequential order that matches clinical inference from prior SM04690 studies regarding the relative therapeutic benefit of each dose. If a test fails to meet the

critical value of $\alpha = 0.05$, all subsequent tests will not be evaluated for the interim efficacy analysis and only be considered as exploratory analysis.

For this study, the pre-specified, fixed hypothesis hierarchy is:

- H1. Change in WOMAC Pain at Week 13, 0.07 mg SM04690 vs Placebo
- H2. Change in WOMAC Pain at Week 13, 0.03 mg SM04690 vs Placebo
- H3. Change in WOMAC Pain at Week 13, 0.23 mg SM04690 vs Placebo
- H4. Change in WOMAC Function at Week 13, 0.07 mg SM04690 vs Placebo
- H5. Change in WOMAC Function at Week 13, 0.03 mg SM04690 vs Placebo
- H6. Change in medial JSW at Week 26, 0.07 mg SM04690 vs Placebo
- H7. Change in medial JSW at Week 26, 0.03 mg SM04690 vs Placebo
- H8. Change in WOMAC Function at Week 13, 0.23 mg SM04690 vs Placebo
- H9. Change in medial JSW at Week 26, 0.23 mg SM04690 vs Placebo
- H10. Change in Patient Global Assessment at Week 13, 0.07 mg SM04690 vs Placebo
- H11. Change in Patient Global Assessment at Week 13, 0.03 mg SM04690 vs Placebo
- H12. Change in Patient Global Assessment at Week 13, 0.23 mg SM04690 vs Placebo
- H13. Change in WOMAC Pain at Week 26, 0.07 mg SM04690 vs Placebo
- H14. Change in WOMAC Pain at Week 26, 0.03 mg SM04690 vs Placebo
- H15. Change in WOMAC Function at Week 26, 0.07 mg SM04690 vs Placebo
- H16. Change in WOMAC Function at Week 26, 0.03 mg SM04690 vs Placebo
- H17. Change in WOMAC Pain at Week 26, 0.23 mg SM04690 vs Placebo
- H18. Change in WOMAC Function at Week 26, 0.23 mg SM04690 vs Placebo
- H19. Change in Patient Global Assessment at Week 26, 0.07 mg SM04690 vs Placebo
- H20. Change in Patient Global Assessment at Week 26, 0.03 mg SM04690 vs Placebo
- H21. Change in Patient Global Assessment at Week 26, 0.23 mg SM04690 vs Placebo

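### With 10 imputations, avoidable Monte Carlo noise can decide a borderline test in the 21-step sequence; inference stays valid, and 100 imputations would remove most of the noise

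*SAP*

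**What the plan says.** SAP 5.2 states the scope: "Multiple imputation will be utilized for the primary and secondary analyses". That covers all 21 hypotheses in SAP 8.2.1. The number of imputations rests on custom alone: "A total of 10 imputation datasets will be created and analyzed based upon accepted convention". The imputation model is a "regression model with data imputed independently for each timepoint", using the outcome's own baseline and treatment group. Estimates are pooled with variance U-bar + 1.1B, where B has divisor 9. The seed is fixed: "Imputations will be performed with a seed of 201610141".

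SAP 8.2.1 says the familywise error rate is "controlled in the strong sense using the closed, fixed sequence testing method". H1 to H21 are each tested at the full 0.05, two-sided under SAP 8.1.1. After a failure, "all subsequent tests will not be evaluated for the interim efficacy analysis" and later results count as exploratory only. SAP 8.3 adds that the interim efficacy analyses are not rerun at the end of the study, so this one imputation run supplies the confirmatory result.

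Neither document gives an expected missing rate, a limit on Monte Carlo error, or a check with more imputations. SAP 5.2 reports the error due to imputation but attaches no action to it.

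**The concern.** Multiple imputation draws random values, so the pooled estimate, its standard error and the p-value all depend on the random-number stream. The dependence shrinks as the number of imputations grows. At 10 it may still be large enough to move a p-value near 0.05 from one side to the other. In most analyses that would be a cosmetic matter. Here each test is a pass/fail gate, and its outcome settles whether every later hypothesis can be confirmatory. Whether a gate opens should depend on the trial data and as little as possible on which of many equally valid streams was used.

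**Working it through.** **Inputs.** Imputations m = 10 (SAP 5.2). About 445 randomized 1:1:1:1, or about 111 per arm; baseline-final correlation 0.1; stated power 95.8% for pain and 78.5% for function (SAP 2.1). Two-sided 0.05 per test (SAP 8.1.1, 8.2.1). The missing share is not stated, so I assume 5-20%. The 100 per group in the power simulation would imply 1 - 100/111.25 = 10.1%, but that is an inference and not a planned rate.

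**The plan's own figure.** Rubin's multiplier is 1 + 1/m = 1.1 and the divisor of B is m - 1 = 9. Both match SAP 5.2.

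**Fraction of missing information (lambda).** Other visits are not used, and the baseline explains 0.1² = 1% of the outcome variance. Imputation therefore recovers almost nothing, and lambda is close to the missing share.

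**Between-seed SD of the test statistic.** To first order it is sqrt(lambda/m). The estimate of B is also noisy. For a statistic near 2 this adds a second term, giving SD² ≈ lambda/m + lambda² × 2/(m - 1). At 20% missing and m = 10: 0.020 + 0.04 × 2/9 = 0.0289, so SD = 0.17. The simulated columns use 111 per arm, correlation 0.1, Bayesian regression imputation and Rubin pooling.

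| Missing | sqrt(lambda/10) | with noise in B | simulated, m = 10 | sqrt(lambda/100) | simulated, m = 100 |
|---|---|---|---|---|---|
| 5% | 0.071 | 0.075 | 0.07 | 0.022 | 0.02 |
| 10% | 0.100 | 0.111 | 0.11 | 0.032 | 0.04 |
| 15% | 0.122 | 0.141 | 0.15 | 0.039 | 0.05 |
| 20% | 0.141 | 0.170 | 0.17 | 0.045 | 0.06 |

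The figures below use the simpler sqrt(lambda/m), so they slightly understate the noise.

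**Borderline tests, 10% missing, normal approximation.**
- Converged p = 0.05 (z = 1.960). With m = 10 the 95% seed range of z is 1.960 ± 1.96 × 0.100, or p from 0.031 to 0.078. With m = 100 it is 1.960 ± 1.96 × 0.032, or p from 0.043 to 0.058.
- Converged p = 0.04 (z = 2.054, a margin of 0.094). It fails in about 17% of seeds with m = 10 (0.094/0.100 = 0.94 SD) and 0.2% with m = 100 (0.094/0.032 = about 3 SD).
- Converged p = 0.03 fails in about 1.8% of seeds with m = 10. Converged p = 0.06 passes in about 21% with m = 10 and 0.6% with m = 100.

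Across 5-20% missing, the failure rate for converged p = 0.04 with m = 10 runs from 9% to 25%.

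**All data sets.** The chance that a verdict differs from the long-run one is about 0.798 × SD × the density of z at the critical value, where 0.798 is the mean absolute value of a standard normal.
- Function, power 78.5%: the expected z lies 0.789 above the critical value, density 0.292. With m = 10: 0.798 × 0.100 × 0.292 = 2.3%. With m = 100: 0.7%.
- Pain, power 95.8%: distance 1.728, density 0.090. With m = 10: 0.7%. With m = 100: 0.2%.

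A separate simulation at 10% missing and m = 10 found that two seeds disagree in about 1% of data sets for pain and 3% for function at the SAP's effects, and 4.6% at half the pain effect. Two-seed disagreement should be about 1.4 times departure from the long-run verdict, so these agree. Cells held 120-250 data sets, so the simulated rates are approximate.

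**The case against.** The strongest reply is that nothing is invalid. The factor 1 + 1/m is Rubin's allowance for a finite number of imputations, so the standard error already carries this noise. Simulated rejection under the null was 4-5% at m = 10. A seed SD of 0.10 adds 0.10² = 0.01 to a sampling variance of 1, or about 1%. The seed is pre-specified and the run is reproducible. All of this stands, and it limits the point to precision.

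Three stronger readings may tempt a reader, and the documents support none of them.
- *That verdicts are generally unreliable.* Among data sets picked for a long-run p between 0.02 and 0.08, the verdict departs from the long-run one in roughly 15-24% of seeds at 10-20% missing. Those rates are conditional on being borderline; the rates over all data sets are a few percent or less. At the assumed pain effect, H1 is seldom borderline.
- *That one failure suppresses every later test.* SAP 8.2.1 makes later tests exploratory, and SAP 8.1.1 still reports each contrast with unadjusted intervals and p-values. No adaptation follows the interim analysis, and Protocol 10.1 calls the study exploratory.
- *That the sponsor could pick a favorable seed.* SAP 5.2 fixes it.

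Two defenses do not hold. A fixed seed makes the result repeatable, but another equally valid seed could still give the opposite verdict. The tipping-point analysis in SAP 5.2.1 examines departures from missing at random, not Monte Carlo error, and only for the primary analysis in dose groups already significant.

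**Conclusion.** The point holds as a matter of precision. Ten imputations give valid inference with avoidable noise: a between-seed SD of about 0.07-0.17 in the test statistic if 5-20% of values are missing, against about 0.02-0.06 with 100. At 10% missing, the chance per test that the verdict differs from the long-run one falls from about 2% to 0.7% for function and from about 0.7% to 0.2% for pain. Function, with the lower stated power, is the more exposed (H4, H5, H8). I give no figure for the whole chain, because that depends on correlations among the tests that the documents do not supply.

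The size rests on an assumed missing rate, on lambda being close to that rate, on data missing completely at random in the simulations, and on the SAP's stated power. The change is worth making because it is nearly free and a failed gate has consequences for all later tests. It is an optional improvement and not a defect that threatens the trial's conclusions.

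**What to change.** In SAP 5.2, before unblinding for the interim analysis, raise the number of imputations from 10 to 100, keep the seed, and update every term that depends on the number:
- index i = 1, ..., 100;
- Q-bar and U-bar divided by 100;
- B with divisor 99;
- Var(Q-bar) = U-bar + 1.01B.

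Use the same number for the tipping-point imputations in SAP 5.2.1, so that the primary and sensitivity runs carry similar noise. The figure of 100 is not unique. A pre-specified limit on the Monte Carlo error of the p-value, with the number raised until it is met, would serve the same end.

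The estimand, analysis model, test order and alpha are unchanged. The cost is computing time only. The noise falls about threefold (sqrt(10) = 3.2) but does not vanish.
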